6.3.3 Screening

See 6.3.2.

6.3.4 Enrollment

See 6.3.2.

6.3.5 On Study Visits

Qualitative interviews will be conducted in Specific Aim 1, Phase 1, and will take approximately 30-45 minutes. A Design Thinking Workshop will be convened during Specific Aim 1, Phase 2 and will take approximately 2-4 hours. Pilot implementation in Specific Aim 2 will follow the PLWD and care partners for 3 months post-ED visit.

6.3.6 End of Study and Follow-up

Participants will be assessed up to 3 months post-ED visit regarding outcomes through surveys built into the AI platform. There is no in-person follow-up.

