4.1 Hypothesis

Specific Aim 1: We will optimize the NeuViCare AI + care coach intervention, for subsequent pilot testing.

Specific Aim 2: We will demonstrate: 1) feasible and acceptable implementation of NeuViCare AI + care coach intervention, 2) care plan adherence and NeuViCare AI engagement, and 3) reduced 30-day care partner burden and PLWD healthcare utilization.

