5.2.2 Secondary and Exploratory Outcome Variables (if applicable)

Participants will be measured regarding their healthcare utilization, including ED visits, hospitalizations and care plan adherence with follow-up in the outpatient setting (secondary outcome). Finally, implementation outcomes of the NeuViCare AI technology will be

assessed through validated surveys of acceptability, appropriateness, feasibility, and usability (secondary outcome).

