For Specific Aim 2 (pilot testing), similar in-ED recruitment strategies will be used as above for identification, consent, cognitive screening, follow-up scheduling, and nominal gift card incentivization, but an additional method of recruitment will also be employed in this phase of the research. To broaden our potential participant pool (particularly when the RA is not in the ED), we will work with the JDAT team to obtain a Dashboard/list of ED patients that meet inclusion criteria. The JDAT team will query the electronic medical record to identify patients with a problem list diagnosis of ‘dementia’ that were discharged from the ED sites. The Dashboard/list of patients will be securely provided to the research team’s RA. The research team’s RA will then use EPIC In-Basket function to contact one of three clinicians with a recent and/or longitudinal relationship with the patient and/or caregiver, outside of the treating ED physician. Clinician #1 is the patient’s PCP, clinician #2 is the ED case manager, and clinician #3 is the ED follow-up nurse. The ED case manager, if involved in the patient’s care, has a longitudinal relationship that lasts up to 72 hours beyond emergency care, in which the patient or caregiver is able to contact them to address issues. In their current role, the ED follow-up nurse already contacts all patients >65 years of age discharged from the ED within 24-48 hours. If the enrolling RA is not present in the ED, the ED case manager or ED follow-up nurse during their interaction will briefly mention the study goals and inquire if the research team’s RA can contact them by telephone to further discuss the study. If for some reason, the case manager or follow-up nurse did not meet with a patient with dementia

identified through the JDAT Dashboard, then we will ask the patient's PCP through EPIC In-Basket if acceptable to contact the patient and caregiver. The research team's RA will then contact the patient and/or caregiver, first informing them that one of the 3 listed clinicians stated it was acceptable for the RA to contact them, followed then by describing the study, identifying interest, and consenting the patient and/or caregiver as described previously (similar to in-ED enrollment from here forward).

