6.3.7 Removal of subjects

Engagement with the study is voluntary. If a participant wishes to withdraw, they will stop using the NeuViCare AI software and not complete follow-up surveys.

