6.4 Statistical Method

6.4.1 Statistical Design

Recorded interviews will be professionally transcribed. We will perform coding throughout the study using a qualitative descriptive approach with thematic analysis. A draft code key will be generated through an inductive coding process. Interviews and coding will occur concurrently, and coding disagreements will be resolved by group consensus. We will use the final code key to analyze the remaining transcripts, and will then produce code reports and identify themes while maintaining an audit trail of coding decisions. NVivo, a specialized software package for qualitative research, will be used to facilitate data organization and theme identification.

Additionally, we will use a primarily inductive approach to content analysis whereby theoretical insights will be developed from the design thinking workshop data. Similar to prior qualitative work within design thinking workshops, themes and subthemes will be generated and grouped by common words, phrases, or ideas.

Regarding the DKAS and Zarit Caregiver burden scale, we will compare baseline and 30-day mean scores of the pilot group using the paired t-test. Given the proposal's pilot nature, descriptive statistics will be used to assess ED and hospitalization outcomes as well as survey data regarding implementation outcomes. A mean score of ≥ 4 using the FIM will be indicative of NeuviCare AI's feasibility. A mean score of ≥ 4 using the AIM will be indicative of NeuviCare AI's acceptability. A mean score of ≥ 4 (using the IAM will be indicative of NeuviCare AI's appropriateness. In analyzing usability data, the 10-item SUS has a possible original score of 0-40. After multiplication by 2.5 and conversion to a 0-100 scale, prior research suggests that above average usability are interventions with a score ≥ 68 .

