6.4.5 Handling of Missing Data

Missing data will be considered missing at random and will not be imputed.

7 Trial Administration

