7.5 Data Collection

Data will be collected using the NeuViCare AI app.

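### The follow-up surveys sit inside the app being rated and missing scores are taken as missing at random, so the AIM, IAM, FIM and SUS means may over-represent people who kept using it

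*Combined protocol and SAP*

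**What the plan says.** Five parts of the combined protocol and SAP bear on this.

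- **Route.** Section 6.3.6: "Participants will be assessed up to 3 months post-ED visit regarding outcomes through surveys built into the AI platform". It also rules out in-person follow-up. Section 7.5 reads in full: "Data will be collected using the NeuViCare AI app". Section 5.2.1 plans contacts at 7 days, 30 days and 3 months for the primary-outcome domains but does not say how contact is made.
- **Withdrawal.** Section 6.3.7: "If a participant wishes to withdraw, they will stop using the NeuViCare AI software and not complete follow-up surveys". Nothing is said about people who drift away from the app without withdrawing.
- **Missing data.** Section 6.4.5: "Missing data will be considered missing at random and will not be imputed". Section 6.4.4 lists no covariates.
- **Benchmarks.** Section 5.2.2 says the technology will be "assessed through validated surveys of acceptability, appropriateness, feasibility, and usability (secondary outcome"). In section 6.4.1 the feasibility rule begins "A mean score of ≥ 4 using the FIM will be indicative of NeuviCare". The same cut-off of 4 applies to AIM and IAM, and 68 on the 0–100 scale applies to SUS. The analysis is descriptive.
- **Engagement.** Section 4.1 lists "care plan adherence and NeuViCare AI engagement" among the things Aim 2 is to demonstrate, but section 6.4.1 contains no engagement analysis.

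No time point or intended respondent is stated for AIM, IAM, FIM or SUS. Section 5.3.1 gives about 25 for the pilot without saying whether these are patients, care partners or pairs, and section 5.3 requires a smart device of care partners only.

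**The concern.** The product being rated is also the only stated route for returning the rating. Several SUS items ask about complexity, confidence and the need for technical help. A person who struggles with the app, or has stopped opening it, may be less likely to reach the questionnaire that would record this.

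The missing-data rule does not help. Missing at random protects an analysis that conditions on observed variables related to response. Here there is no imputation, no covariate and no model, so each benchmark is an unadjusted responder mean. In general that mean is unbiased only if answering is unrelated to the score.

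These outcomes are secondary and no go/no-go decision hangs on them. They are nevertheless the only stated criteria for calling the app feasible, acceptable, appropriate or above average in usability, and the synopsis describes a trial aimed mainly at functionality and usability. The plan does not promise responders out of those expected, so a reader could not tell whom a benchmark result represents. The 30-day DKAS and Zarit comparisons share the problem only if they too are collected in the app, which section 5.2.1 leaves open.

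**Working it through.** **Is there a figure to reproduce?** No. Section 6.4.2 (sample size) is marked not applicable, and no dropout or response rate is given. The scale arithmetic is consistent: SUS 40 × 2.5 = 100.

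**Inputs from the documents.** Benchmarks B = 4 (AIM, IAM, FIM) and B = 68 (SUS), from section 6.4.1. Pilot size about 25, from section 5.3.1.

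**Assumed inputs.** Number missing m = 2, 5 or 8 of 25 (8%, 20%, 32%). Observed responder means O = 4.1, 4.2, 4.5 and SUS 70, 72, 75. The 5-point items are taken as coded 1 to 5. For SUS the fractions are of people who used the app at least once.

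**Tipping point.** With f = m/25, the full-group mean is (1 − f) × O + f × v, where v is the non-responder mean. Setting this equal to B gives

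v* = (25B − (25 − m)O) / m.

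The full-group mean misses the benchmark if non-responders would average below v*. No non-responder score has to be assumed.

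With m = 5:
- O = 4.2: (100 − 20 × 4.2)/5 = (100 − 84)/5 = 3.20.
- SUS 72: (1700 − 20 × 72)/5 = (1700 − 1440)/5 = 52.0.

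| Benchmark | Observed mean | 2 missing | 5 missing | 8 missing |
|---|---|---|---|---|
| ≥ 4 | 4.1 | 2.85 | 3.60 | 3.79 |
| ≥ 4 | 4.2 | 1.70 | 3.20 | 3.58 |
| ≥ 4 | 4.5 | cannot tip (−1.75) | 2.00 | 2.94 |
| ≥ 68 | 70 | 45.0 | 60.0 | 63.8 |
| ≥ 68 | 72 | 22.0 | 52.0 | 59.5 |
| ≥ 68 | 75 | cannot tip (−12.5) | 40.0 | 53.1 |

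Only f matters, so reading 25 as pairs changes nothing: 10 of 50 gives the same values as 5 of 25.

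**Smallest fraction missing that could tip the result**, with every non-responder at the scale minimum L: f = (O − B)/(O − L).
- Observed 4.1, 4.2, 4.5 (L = 1): 0.1/3.1 = 3.2%, 0.2/3.2 = 6.25%, 0.5/3.5 = 14.3%.
- SUS 70, 72, 75 (L = 0): 2/70 = 2.9%, 4/72 = 5.6%, 7/75 = 9.3%.

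**Illustrative simulation.** All inputs are assumed: 25 enrolled, normal scores with SD 0.8 limited to 1–5, true mean 3.78, 70% responding. The chance that the observed mean reaches 4 is 0.07 with full response and 0.11 if response is unrelated to score. It is 0.43 if the log-odds of responding rise by 1 per SD of score, and 0.68 if they rise by 2. This shows that the mechanism can matter at this sample size; it does not predict what will happen.

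**The case against.** The strongest reply is that the bias needs a chain of events the documents do not establish: people lapse before the scales are given, and then fail to answer because of what they think of the app. The scales may be given early. Section 6.3.5 follows participants for 3 months with no condition of continued use, so someone who lapses arguably stays in follow-up. Care-coach sessions continue after discharge, and Aim 2 carries over "consent, cognitive screening, follow-up scheduling, and nominal gift card incentivization", all of which may hold response up. The platform can be reached by phone, tablet or computer and one component sends text messages, so a survey may reach people who no longer use the app. Section 7.5 cannot be exclusive, since screening tests, interviews and chart review take place outside the app. Some non-response will come from illness or death rather than opinion. Finally, this is a small descriptive pilot, and the missing-at-random sentence changes no estimate.

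Much of this stands as a limit on size. Lapsed use is not the same as non-response, and the timing is unknown. An observed 4.2 with 20% missing tips only if non-responders average a full point lower, and the documents do not suggest a gap of that size. Deaths should be counted separately rather than given a hypothetical score.

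It does not remove the problem. None of these features is a stated off-app route for these surveys, the planned contacts have no stated mode and name only the primary domains, and none supplies a denominator. That the missing-at-random sentence changes no estimate is part of the point: it offers reassurance without adjustment.

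**Conclusion.** The concern holds. The plan ties the return of ratings to the product being rated, gives no other survey route, and covers the resulting gaps with an assumption that does not protect an unadjusted responder mean. The benchmark means may therefore over-represent people who kept using the app.

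How far cannot be determined from the documents. With few missing and a clear margin (4.5 or SUS 75 with 2 of 25 missing) the conclusion cannot be overturned. With 20% or more missing and a mean just above the mark, a modest difference is enough: at 4.1 with 5 missing, non-responders need average only half a point lower (3.60). These figures rest on assumed observed means and missing fractions. Confidence is medium: the mechanism is plain in the text, but its size is unknown. It should be fixed, because the remedy is cheap and these scales carry the trial's usability and feasibility conclusions.

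**What to change.** 1. **Sections 6.3.6 and 7.5, reconciled with 5.2.1.** Have the existing research assistant offer the surveys by telephone or a non-app link to every enrolled participant who has not withdrawn consent, whether or not they still use the app. Record the mode. Fix one time point and the intended respondent for AIM, IAM, FIM and SUS.
2. **Section 6.3.7.** Separate stopping the app from withdrawing from follow-up.
3. **Section 6.4.5.** For these scores, replace reliance on missing at random with reported denominators. For AIM, IAM and FIM, give responders out of all enrolled intended respondents. For SUS, give responders out of all who used the app at least once, with never-users as a count, because its items presuppose use. Count deaths separately. For each benchmark, report the non-responder mean at which it would no longer be met, and use that to qualify the conclusion.

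**Cost.** Protocol wording, which section 7.2 makes subject to an approved IRB amendment before implementation, and some telephone time for about 25 enrolled; the research assistant already telephones care partners. App and telephone answers may differ in either direction, which is why mode must be recorded. Part 3 needs no field work.

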2.1.1 Device Preclinical Experience

As a way to address many of these unmet caregivers' needs and poor patient outcomes, Amicus Brain Innovations, Inc. a technology start-up company, has created NeuViCare, which is a soon-to-be commercially available AI-led, assistive and decision support online service application that can be accessed from a smart phone, tablet or computer by clinicians, patients and caregivers. It was designed to reduce caregiver load and increase patient adherence rates for better quality of life.

NeuViCare's multifunctional platform services are designed to impact caregiver load, while addressing their unmet needs and patients' quality of life through AI-led technology.

NeuViCare Task-Support Service will increase care plan adherence rates and allow for more timely diagnoses by providing an interactive, appointment reminder service. NeuViCare Resource Advisor will educate caregivers about available resources and reduce their time spent on this task by providing context-sensitive, task-support services to reliable community resources. NeuViCare Community will provide a secure, online forum that will provide peer-support and increase caregivers knowledge on challenging behaviors by administering weekly educational series and just-in time answers provided by AI. Amicus Brain will provide technical support and troubleshoot any issues with the community software.

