5.2 Outcome Variables

5.2.1 Primary Outcome Variables

After in-ED enrollment, we will collect baseline measurements of PLWD and their care partners. Particularly, at time 0 this will include domain assessments of validated tools addressing dementia knowledge, PLWD self-efficacy, psychological well-being, social connectedness, and caregiver experience. After ED- or hospital-community care transition, a virtual session led by the care coach will build upon discharge instructions by developing a comprehensive transdisciplinary care plan and integrating the use of NeuViCare AI technology. Subsequent sessions with the PLWD and their care partner will assess knowledge translation of NeuviCare AI, follow through with care plan, and the development of sustainable skills for preventing crisis and recidivism. At follow-up time points of 7 days, 30 days, and 3 months, participants will be contacted to reassess responses to above domains of interest (primary outcome).

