6.1 Treatment – Device

6.1.1 Intended Use for Device (provide the following information for each device being investigated in the study)

Building upon prior work in the outpatient Neurology setting, NeuViCare AI will include variations of its 5 components: 1) NeuViCare Planner - enables review of ordered tests and external resources recommended by the care provider; 2) NeuViCare Task-Support Service - provides context-sensitive, personalized SMS text-based assistance to help patients' complete care plan captured in the NeuViCare Planner; 3) NeuViCare Resource Advisor - presents trusted, unbiased advice to locate nearby resources listed within their care plan; 4) NeuViCare Advisor - educates and trains PLWD and their care partners at the moment of need; and 5) NeuViCare Community Hub - a safe virtual space which enables care partners to interact with other peer care partners to gain their experiential knowledge and emotional support.

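### The 30-day dementia knowledge scale (DKAS) is to be collected in the app that also teaches and answers, with no unaided-answer condition, so part of any gain could be access rather than learning

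*Combined protocol and SAP*

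**What the plan says.** Outcome collection at follow-up is placed in the app. Section 6.3.6 states: "Participants will be assessed up to 3 months post-ED visit regarding outcomes through surveys built into the AI platform", and adds: "There is no in-person follow-up". Section 7.5 says of data in general: "Data will be collected using the NeuViCare AI app". It makes no exception for any instrument or time point.

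The app is also a source of teaching and answers. Section 2.1.1 lists a weekly educational series and "just-in time answers provided by AI" under the Community component, in connection with challenging behaviors. Section 6.1.1 describes an Advisor component that "educates and trains PLWD and their care partners at the moment of need".

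Dementia knowledge is among the primary-outcome domains. Section 5.2.1 lists baseline assessments "addressing dementia knowledge, PLWD self-efficacy, psychological well-being, social connectedness, and caregiver experience", and continues: "At follow-up time points of 7 days, 30 days, and 3 months, participants will be contacted to reassess responses to above domains of interest". Section 6.4.1 gives the only planned hypothesis tests: "Regarding the DKAS and Zarit Caregiver burden scale, we will compare baseline and 30-day mean scores of the pilot group using the paired t-test". The Synopsis describes one open-label arm, and section 5.3.1 plans about 25 pilot participants.

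**The concern.** A knowledge score can be raised in two ways: the person knows more, or the person has help while answering. The plan puts the follow-up assessment in the tool that is meant to provide such help, and says nothing about answering without it.

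The opportunity for help is probably not equal at the two ends of the paired comparison. Around baseline, participants have had at most the introductory instructions given in the ED (6.1.2). By 30 days they are expected to have had care-coach sessions that integrate the app into their care plan (5.2.1, 6.1.2). If help is used more at 30 days, the difference shifts upward. With one arm, no control group can separate that shift from learning.

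At stake is the reading of one of only two tested scales. A significant DKAS change would naturally be reported as improved dementia knowledge. This is a measurement question among people who do respond, and it is distinct from loss to follow-up. It applies to the knowledge scale and not in the same way to the self-reported Zarit burden scale.

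**Working it through.** **The passages side by side**

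1. *Follow-up mode.* Sections 6.3.6 and 7.5 put follow-up data in the app. Neither names the DKAS, so its in-app completion follows from their general wording. Section 5.2.1 says participants are contacted but names no other channel.
2. *Help in the app.* Sections 2.1.1 and 6.1.1 describe education and answers as designed functions.
3. *Conditions of the test.* No section gives a closed-book instruction, a lock on help content, supervision, or a log of app use during the survey.
4. *Exposure.* Introduction only around baseline (6.1.2); coached use by 30 days (5.2.1, 6.1.2).

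**What a look-up shift would do to the planned test**

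The plan has no figure to reproduce: section 6.4.2 on sample size is marked not applicable, and no DKAS SD, expected change or significance level is given. The following is an illustration.

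Inputs: n = 25 pairs (5.3.1, assuming every pilot participant contributes a pair). Assumed: two-sided alpha 0.05, equal SDs at the two times, correlation r = 0.6 between baseline and 30 days, zero true learning, and a look-up shift of s score SDs at 30 days only.

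Standardized mean change: d = s / √(2(1 − r)). With r = 0.6 the divisor is √0.8 = 0.894.

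Noncentrality: λ = d√n = 5d. The test rejects when |t| exceeds 2.064 on 24 degrees of freedom, that is, when the observed mean change exceeds 2.064/5 = 0.413 SD of the change score. The rejection probability comes from the noncentral t distribution.

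| Shift s | d | λ | Probability of a significant result |
|---|---|---|---|
| 0 | 0 | 0 | 0.05 |
| 0.1 | 0.112 | 0.56 | 0.08 |
| 0.3 | 0.335 | 1.68 | 0.36 |
| 0.5 | 0.559 | 2.80 | 0.76 |

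Sensitivity to the assumptions:

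- r from 0.4 to 0.8, n = 25: 0.07 to 0.12 for s = 0.1; 0.26 to 0.62 for s = 0.3; 0.59 to 0.97 for s = 0.5.
- n = 15 completers, r = 0.6: 0.07, 0.23 and 0.52.
- n = 15, r = 0.4, s = 0.3: 0.17.

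The calculation shows how the planned test responds if a shift exists. It is not evidence that one does.

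**The case against.** The strongest case on the other side is that the asymmetry is not established. Section 7.5 covers data collection without exception and may put baseline in the app too. The order of the baseline assessment and the introduction to the app is not given, and people recruited by telephone after discharge (6.3.2) need not be assessed in the ED at all. Care partners must own an internet-connected device (5.3), so other look-up is possible at any remotely completed assessment. This stands. A reader might infer that the baseline is unaided and that the comparison favours the intervention by construction; the documents do not support that. What remains is a difference in familiarity and coached use between the two times.

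Second, the app's answer function should not be overstated. The just-in-time answers belong to the Community forum and concern challenging behaviors, and 6.1.1 says the study version will use variations of the five components. A reader might picture the answers on the same screen as the survey, but nothing says the Advisor can be reached while a survey is open. The documents never spell out the DKAS or describe its items and scoring, so its use for the knowledge domain, and its sensitivity to look-up, are inferences. This also stands, and it limits the point to a possibility.

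Third, this is a pilot mainly about functionality and usability. Knowledge gain is not in the Aim 2 hypothesis (4.1), no decision rule depends on the DKAS, and an uncontrolled change could not be attributed to the intervention anyway. That lowers the stakes. It does not remove the problem: attribution asks what caused a change in knowledge, whereas here it is uncertain whether the score reflects knowledge at all.

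Finally, access to answers may be the intended benefit. If so, the result should be reported as access.

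**Conclusion.** The point holds as a risk of measurement bias that is cheap to reduce. The plan places follow-up assessment in a platform designed to educate and answer, sets no unaided condition for the DKAS, and tests its change in one arm without a control. Part of any 30-day gain could be access to app content during the test.

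The likely direction is upward at 30 days, because coached use comes after baseline. The size is unknown, and no passage shows that any participant would look answers up. The 8%, 36% and 76% figures rest wholly on the assumed shifts, r = 0.6, 25 complete pairs, alpha 0.05 and no learning. The conclusion also assumes that the general wording of 6.3.6 and 7.5 covers the DKAS, and that the DKAS is a scale on which help can raise the score.

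**What to change.** Amend 6.3.6 and 7.5 so that the DKAS is given in one stated mode at every time point, baseline included, with an instruction to answer without NeuViCare or other help.

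- *Preferred:* the research assistant reads the items, by telephone at the follow-up contacts already planned in 5.2.1. Research assistants already make telephone calls for proxy consent and the AD8 (6.3.2), and no in-person visit is added.
- *If it stays in the app:* close the Advisor, Community and answer functions while the DKAS is open.
- *A separate web link* is acceptable only with the same instruction. It can be opened on the device that runs NeuViCare, so the remaining look-up risk should be acknowledged when a gain is interpreted.

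The cost is protocol wording plus either a little research-assistant time or a small software setting. No participants or visits are added.
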